12.5.2. Reporting of Serious Adverse Events to DAIT/NIAID (Sponsor)

This section describes the responsibilities of the site investigator to report SAEs to the Study Sponsor (NIAID/DAIT) via the AE/SAE eCRF. Timely reporting of adverse events is required by 21 CFR and ICH E6 guidelines.

When a site investigator identifies a SAEs, he or she must notify DAIT/NIAID via the DAIT-SACCC within 24 hours regardless of the relationship or expectedness. Site investigators are to report these events on the SAE eCRF in Electronic Data Capture (EDC). Should EDC become unavailable/ inaccessible, the site investigator should notify DAIT/NIAID via the DAIT-SACCC email at [contact]. This email can serve as the initial notification; however, within the next business day the SAE eCRF must be completed.

All requested information on the SAE eCRF should be provided. Unavailable details of the event at time of initial report should not delay submission of known information. The initial report should include at a minimum: AE term, relationship to tofacitinib, and reason why event is serious (per definitions). Supplementary Case Report Form (CRF) pages including medical history, concomitant medications, demographics, study drug administration, and death must be provided. As additional details become available, the SAE eCRF should be updated and submitted. With each iteration of the form, the investigator (or designated sub-investigator) must sign the form electronically.

For additional information regarding SAE reporting, contact Rho Product Safety (DAIT-SACCC):

Rho Product Safety

12.5.3. Reporting to FDA

This clinical study has been granted exemption from investigational new drug application (IND) regulations by the FDA in accordance with 21 CFR 312.2(b) of the regulations, therefore, AEs will not be reported to the FDA by the study sponsor (NIAID).

12.5.4. Reporting of Adverse Events to IRBs/IECs

In this multi-site study, the investigators shall report adverse events, including expedited reports, in a timely fashion to their respective IRB/IEC in accordance with applicable regulations and guidelines.

12.6. Pregnancy Reporting

The investigator shall be informed immediately of any pregnancy in a study participant or a partner of a study participant. A pregnant study participant shall be instructed to stop taking study medication immediately. A study participant whose partner is pregnant shall be advised to inform the partner's obstetrician about the trial. The investigator shall counsel the participant and discuss the risks of continuing with the pregnancy and the possible effects on the fetus. Monitoring of the pregnant participant shall continue until the conclusion of the pregnancy. Additionally, pregnant participants and partners should be given information about Mother to Baby. The current patient information fact sheet on tofacitinib can be found at the following link: <https://mothertobaby.org/fact-sheets/tofacitinib-pregnancy/>

The investigator shall report to DAIT/NIAID via the DAIT-Statistical and Clinical Coordinating Center (SACCC) within 1 business day of becoming aware of the event using the Pregnancy eCRF. All pregnancies in study participants identified during the study shall be followed to conclusion and the outcome of each must be reported. Pregnancies in the partners of study participants do not have to be followed to conclusion; however, the status of the partner should be reported at the last study visit, if known. The Pregnancy eCRF shall be updated and submitted to the DAIT-SACCC when details about the outcome are available. When possible, similar information shall be obtained for a pregnancy occurring in a partner of a study participant.

Information requested about the delivery shall include:

- Gestational age at delivery.
- Birth weight, length, and head circumference.
- Gender.
- Appearance, pulse, grimace, activity, and respiration (APGAR) score at 1 minute, 5 minutes, and 24 hours after birth, if available.
- Any abnormalities.

All pregnancy complications that result in a congenital abnormality, birth defect, miscarriage, and medically indicated abortion - an SAE shall be submitted to the DAIT-SACCC using the SAE reporting procedure described above (Section 12.5.1, *Reporting of Serious Adverse Events to DAIT/NIAID*).

12.7. Reporting of Other Safety Information

An investigator shall promptly notify DAIT/NIAID via the DAIT-SACCC when an “unanticipated problem involving risks to participants or others” is identified, which is not otherwise reportable as an adverse event.

12.8. Review of Safety Information

12.8.1. Medical Monitor Review

The DAIT/NIAID Medical Monitor shall receive monthly reports from the DAIT-SACCC compiling new and accumulating information on AEs, SAEs, and pregnancies recorded by the study site on appropriate eCRFs.

In addition, the Medical Monitor shall review and make decisions on the disposition of the SAE and pregnancy reports received by the DAIT-SACCC (See Sections 12.5.1, *Reporting of Serious Adverse Events to DAIT/NIAID*, and 12.6, *Pregnancy Reporting*).

12.8.2. Data Safety and Monitoring Board Review

12.8.2.1. Planned DSMB Reviews

The progress of the study will be monitored by the NIAID Data and Safety Monitoring Board (DSMB). The DSMB shall review safety data at least yearly during planned DSMB Data Review Meetings. Data for the planned safety reviews will include, at a minimum, a listing of all reported AEs and SAEs. The DSMB will also be informed of any Expedited Safety Reports during planned safety reviews.

In addition, the DSMB will be notified of any notable impacts on the study due to COVID-19 (See Section 3.1.1, *Considerations Regarding COVID-19*.)

12.8.2.2. Ad hoc DSMB Reviews

In addition to the pre-scheduled data reviews and planned safety monitoring, the DSMB may be called upon for *ad hoc* reviews. The DSMB will review any event that potentially impacts safety at the request of the protocol chair or DAIT/NIAID. In addition, the following events will trigger an *ad hoc* comprehensive DSMB Safety Review:

- Any death considered possibly or definitely related to study treatment or procedures.
- The occurrence in 2 participants of Grade 3 or higher AEs or SAEs with the same MedDRA preferred terms considered at least possibly related to study treatment or procedures.
- The occurrence in 2 participants of Grade 3 or higher infections.
- Any grade 2 or higher thromboembolic event.

After review of the data, the DSMB will make recommendations regarding study conduct and/or continuation.

12.8.2.2.1. Temporary Suspension of Tofacitinib Dosing for ad hoc DSMB Safety Review

If a triggering event occurs and an ad hoc DSMB Safety Review is required (Section 12.8.2.2, *Ad hoc DSMB Reviews*), then a temporary halt in initiating dosage for new enrollees will be implemented. Participants on study treatment will continue as planned. If two weeks has elapsed and the ad-hoc DSMB has not met, then no new participants will be consented or enrolled until after the DSMB completes review of the safety data.

13. Statistical Considerations and Analytical Plan

13.1. Overview

This is a single-arm multi-site proof-of-concept study in which participants with CLE will undergo 25 days of treatment with tofacitinib (11 mg daily PO). The primary objective is to determine the impact of tofacitinib on photosensitivity parameters, including UVB-mediated cutaneous apoptosis, UVB-mediated inflammatory gene transcription, and MED in response to UVB exposure. The study will also evaluate changes in clinical endpoints and safety.

13.2. Endpoints

Primary and secondary endpoints are listed in Sections 3.2, *Primary Endpoint* and 3.3, *Secondary Endpoints*.

13.3. Measures to Minimize Bias

This study includes well-defined entry criteria to ensure the target population is correctly identified. Although the study has a single open-label arm, the photosensitivity parameters, which are key to evaluating the primary objective, are all objectively measured and not subject to participant or investigator bias. To minimize the potential threat to study integrity by loss of participants between the first and second phototests/biopsies, assessments are kept to minimum, and attention will be paid to participant well-being during and after procedures.

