3.4. Stratification, Randomization, and Blinding/Masking

This is a single-arm open-label study. There are no plans for stratification, randomization, or masking.

4. Selection of Participants

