8.1.1. Exception to Visit Window Rules

For participants who complete phototesting and the biopsy at Visit 1 (Day 0) and Visit 2 (Day 1), Visit 4 (Day 25) may be delayed up to 12 weeks after Visit 1 (Day 0), if necessary. This may occur if study therapy compliance criteria, as described in *Section 8.5.5, Research Assessments*, have not been met.

If it is necessary to start a new 25-day course of tofacitinib as described in *Section 6.6, Resumption of Investigational Product*, the participant will have a virtual visit 14 days after reinitiating tofacitinib to assess adverse events.

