If a participant fails to bring the IP pill bottle(s) back at Visit 4 (Day 25), UVB exposure may proceed during this visit. However, site personnel must confirm at least 84% compliance via a visual pill count prior to the erythema assessment and biopsy at Visit 5 (Day 26). If 84% compliance is not achieved, participant may resume IP dosing. Once the participant has completed appropriate IP dosing, the UVB exposure will be conducted on a site on the lower back, above the original. If the participant does not take the final dose of IP the morning of Visit 5 (Day 26), the erythema assessment and biopsy will still take place, as long as the participant is compliant with their IP dose the 7 days prior to Day 26.

- **Erythema Assessment:**

At Visit 2 (Day 1) and Visit 5 (Day 26), erythema levels for unexposed skin and each template square of the UVB-exposed skin will be quantified using a Chroma Meter (Minolta Model CR-400 or equivalent device). To determine the MED, first compute the average of all the unexposed skin's a* (redness) readings and add 2.5. The lowest exposure with the site's average a* (redness) readings at or above this value is the MED. All skin types (except for Fitzpatrick VI) can be expected to show a response within the planned exposure range[26].

- **Skin Biopsy:** At the indicated time points, 6mm-diameter punch biopsies of nonlesional skin are planned at 3 sites as follows:

1. On Visit 2 (Day 1), 3 biopsy sites on the right buttock include (1) unexposed skin, (2) skin exposed to the 1x MED, and (3) skin exposed to the UVB dose that is 1 step higher than the 1x MED.
2. On Visit 5 (Day 26), 3 biopsy sites on the left buttock will be comparable to those taken on Visit 2 (Day 1), including (1) unexposed skin, (2) skin exposed to the same UVB Dose as the 1x MED from the Visit 2 (Day 1) assessment, and (3) skin exposed to the UVB dose that is 1 step higher than the 1x MED from the Visit 2 (Day 1) assessment. If the 1x MED from the Visit 2 (Day 1) assessment is at the highest UVB dose (80mJ/cm²) or if no erythema is detectable on exposed skin at any dose, then two 4mm biopsies of skin exposed the highest UVB dose will be taken at both Visit 2 (Day 1) and Visit 5 (Day 26).
3. Stitch removal is planned for Visit 3 (Day 14) and Visit 6 (Day 40).

Table 8.2. Schedule of Events

Time Point	Screening	Visit 1	Treatment				Visit 6	Early Termination Visit	Restart Visit ^H	Unscheduled Visit

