D. See Section 3.1, *Description of Study Design*, for information regarding the timing of IP dosing.

E. See Section 8.5.5, *Research Assessments*, regarding the compliance requirements for phototesting, erythema assessment and biopsy.

F. As needed.

G. Laboratory assessments as relevant to the reason for the Unscheduled visit. These labs must be drawn prior to reinitiating study drug if the participant has had a pause or interruption in IP dosing.

H. In order to reassess entry criteria, all labs will be performed STAT. Once eligibility has been reconfirmed, tofacitinib will be dispensed. The first dose of the new course of tofacitinib will be taken the following day.

9. Mechanistic Assays

Studies on skin biopsies

1. RNA sequencing to identify changes in inflammatory gene expression before and after UV exposure before and after tofacitinib.
2. TUNEL, 8-hydroxyguanosine, and caspase-3 staining to evaluate for cell death before and after UV exposure before and after tofacitinib.
3. Spatial sequencing to evaluate the inflammatory cell populations before and after UV exposure before and after tofacitinib.
4. VgII3 localization in biopsies before and after UV exposure before and after tofacitinib to understand how this regulator of female bias in autoimmunity is modulated in lupus.

Studies on blood

1. Activation of neutrophil NETosis before and after tofacitinib.

10. Biospecimen Storage

1. Formalin Fixed, paraffin-embedded (FFPE) skin biopsies collected as part of this study will be retained for up to 15 years.
2. Plasma from treated participants will be stored for contribution to approved other collaborative projects.
3. Peripheral blood mononuclear cells (PBMCs) from studies left over from neutrophil isolation will be frozen and stored in LN₂ for additional analysis.

11. Criteria for Participant and Study Completion and Premature Study Termination

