13.4. Analysis Plan

13.4.1. Analysis Populations

The **Safety Sample (SS)** population includes all participants who receive any amount of tofacitinib.

The **Per Protocol 1 (PP1)** population includes all participants who receive any amount of tofacitinib and who complete phototests and skin biopsies at both baseline (Visits 1 and 2) and post-treatment (Visits 4 and 5) time points. Only individuals who complete at least 21 days of IP dosing will have the post-treatment phototest. The primary objective of this proof-of-concept study cannot be evaluated in individuals who do not have data at both pre- and post-treatment time points.

The **Per Protocol 2 (PP2)** population includes all PP1 participants with no protocol deviations that would impact photo sensitivity assessments. The reported major deviations will be reviewed during a masked data review to determine which participants should be excluded from the PP2 population.

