13.4.2. Primary Analysis of Primary Endpoint

The primary endpoint is change in percentage of UVB-induced apoptotic epidermal cells from Visit 2 (Day 1) (pre-treatment) to Visit 5 (Day 26) (post-treatment). Percentage of UVB-induced apoptotic cells (A^{UVB}) is defined as the number of TUNEL positive cells in the epidermis divided by the number of nuclei in that high powered field. The percentage of UVB-induced apoptotic cells at a visit is defined as the difference between the percentage of apoptotic epidermal cells in the biopsy exposed at the MED ($A^{Day1MED}$) and percentage of apoptotic epidermal cells in the unexposed biopsy ($A^{unexposed}$), for both biopsies taken at the same visit. The change in percentage of UVB-induced apoptotic epidermal cells will be computed as follows for each individual in the study:

$$A_{Day\ 1}^{UVB} = A_{Day\ 1}^{Day1MED} - A_{Day\ 1}^{Day\ 1\ unexposed}$$

$$A_{Day\ 26}^{UVB} = A_{Day\ 26}^{Day1MED} - A_{Day\ 26}^{Day\ 26\ unexposed}$$

$$\text{change in } A^{UVB} = A_{Day\ 26}^{UVB} - A_{Day\ 1}^{UVB}$$

The null and alternative hypotheses for the primary analysis of the primary endpoint are:

H_0 : Mean change in $A^{UVB} = 0$

H_A : Mean change in $A^{UVB} \neq 0$

The statistical hypotheses outlined above for the mean change in A^{UVB} will be evaluated in the PP1 population using a two-sided Wilcoxon signed-rank test at a Type 1 error rate of 0.05.

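### The TUNEL count behind the primary endpoint has no visit-masked reading, and Section 13.3's claim that it is free of investigator bias rests on no procedure

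*Combined protocol and SAP*

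**What the plan says.** Section 13.3 meets the open-label, single-arm design with an assertion: the photosensitivity parameters "are all objectively measured and not subject to participant or investigator bias". Section 3.4 states: "There are no plans for stratification, randomization, or masking".

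Section 13.4.2 builds the primary endpoint on the "number of TUNEL positive cells in the epidermis divided by the number of nuclei in that high powered field". At each visit the unexposed percentage is subtracted from the percentage in the biopsy exposed at the Day 1 MED. The endpoint is the Day 26 difference minus the Day 1 difference, tested against zero with a two-sided Wilcoxon signed-rank test.

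Section 9 lists the assay only as "TUNEL, 8-hydroxyguanosine, and caspase-3 staining to evaluate for cell death before and after UV exposure before and after tofacitinib". Neither section says who reads the slides, whether the reader knows the visit, how fields are chosen, whether counting is manual or automated, or whether the two visits are stained together.

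Masking appears in one other place, the definition of the PP2 population in Section 13.4.1: "The reported major deviations will be reviewed during a masked data review". That concerns who enters a supportive analysis, not how slides are read.

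**The concern.** Counting positive cells in a high powered field involves choosing the field and deciding, or setting a threshold for, what counts as positive. Both can shift if the reader knows that a slide was taken after treatment. The Section 13.3 claim is reasonable for MED, which Section 8.5.5 obtains from Chroma Meter redness readings and a fixed numerical rule, and for RNA transcript counts. It does not carry over to a microscopy count with no stated safeguard.

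Visit and treatment coincide completely in this design: Day 1 is always before drug and Day 26 always after. With no concurrent control, a reading error tied to visit cannot be separated from an effect of tofacitinib. MED and RNA are supportive secondary measures and do not protect the primary test.

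**Working it through.** **Inputs.** n = 10, two-sided signed-rank test at 0.05 (Sections 13.4.2 and 13.7). Mean apoptosis 50% in UVB-exposed and 6% in unexposed cells (Table 13.1). SD of change 15 points (best estimate), with 20 and 30 also taken from Section 13.7. The relative reading error r is an assumption; the documents give no figure, so 10% and 20% are shown.

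**The plan's own power figure.** With n = 10 the exact test rejects when the rank sum is ≤8 or ≥47, an actual size of 0.0488. For a 20-point change and SD 15, simulated power is 95.4% (normal), 94.1% (logistic), 92.4% (double exponential) and 95.7% (uniform). This agrees with the stated minimum of 93% to within a point, so the set-up matches the plan's.

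**What the subtraction removes.** Suppose the drug does nothing. Day 1 gives 50 − 6 = 44 points.

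- Additive error a on both Day 26 slides: (50 − a) − (6 − a) = 44. Change = 0; the error cancels.
- Proportional under-calling r on both Day 26 slides: 50(1 − r) − 6(1 − r) = 44(1 − r). Change = −44r, which is −4.4 points at r = 10% and −8.8 at r = 20%.
- Under-calling of the exposed Day 26 slide only: 50(1 − r) − 6 = 44 − 50r. Change = −50r, which is −5 or −10 points.

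**Chance of p<0.05 with no true effect** (normal changes, 1,000,000 simulated trials per cell):

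| Reading error on Day 26 slides | Shift (points) | SD 15 | SD 20 | SD 30 |
|---|---|---|---|---|
| None, or common additive | 0 | 4.9% | 4.9% | 4.9% |
| Both slides, r = 10% | 4.4 | 13% | 9% | 7% |
| Both slides, r = 20% | 8.8 | 37% | 23% | 13% |
| Exposed slide only, r = 10% | 5 | 15% | 11% | 7% |
| Exposed slide only, r = 20% | 10 | 45% | 28% | 15% |

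**Against the 20-point benchmark.** For both-slide error to create a mean change of 20 points by itself, r = 20/44 ≈ 45%. The chance of p<0.05 together with an observed mean drop of at least 20 points, with no true effect, at r = 10% and 20% is:

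- SD 15: about 0.05% and 0.9%
- SD 20: about 0.7% and 3.7%
- SD 30: about 3.3% and 8.2%, against 1.1% with no reading error

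**The case against.** There is a fair case on the other side.

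- **Section 3.4 is probably about treatment.** It sits with randomization and stratification. This is accepted, but no other section supplies masked slide reading.
- **Specimens are coded.** Section 5.4 gives them a participant-specific number, Section 17.3 replaces names with numbers, and Section 15 has central laboratories send electronic data straight to the data center. These measures protect identity and data transfer. None hides the visit, and Section 15 does not say that TUNEL is read centrally.
- **The reader may not be a site investigator, or counting may be automated.** Either would weaken the concern. Automation with a fixed threshold takes most of the positive/negative call away from the reader, though not necessarily the choice of field. The documents say neither, and they cite no laboratory manual.
- **The size of the error is assumed.** This is correct. The calculation takes under-calling as uniform and in one direction across participants, and the 50% and 6% means come from cultured keratinocytes, which Section 13.7 expects to resemble skin. The rates show how sensitive the test is, not that bias will occur.
- **Proof of concept is judged at 20 points.** This limits the harm, as the last set of figures shows. It does not remove it, because the formal hypothesis is a change different from zero and that is the test at risk.

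**Conclusion.** The concern holds. The claim in Section 13.3 is unsupported for the TUNEL count, though better founded for MED and RNA. A proportional or exposed-slide reading error tied to visit would survive the subtraction and could not be told apart from a drug effect. At the planning SD of 15, an assumed 10% or 20% under-calling of both Day 26 slides raises the false-positive rate from 4.9% to about 13% or 37%; larger SDs reduce the inflation.

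These rates depend on an assumed r, normally distributed changes and the Table 13.1 means. Reading error of this size would seldom imitate a 20-point effect at SD 15. The omission does not invalidate the design, but the sponsor should correct it because the safeguard costs little and protects the only primary test.

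**What to change.** In Sections 3.4 and 13.3, state that:

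- TUNEL slides carry random codes that do not reveal the visit;
- each participant's Day 1 and Day 26 biopsies are stained and read in one batch, in random order;
- the reader is masked to visit, and to exposure where feasible, until the counts are locked.

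In the same edit, say whether counting is manual or automated and how fields are chosen. Narrow the Section 13.3 statement so that it covers TUNEL only with these safeguards in place; it can stand as written for MED read by Chroma Meter.

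**Cost.** Slides must be relabelled, and someone other than the reader must hold the codes. Day 1 tissue must wait for Day 26 tissue, up to about 12 weeks after Visit 1 if Visit 4 is delayed under Section 8.1.1, so results come later. Section 10 already provides for keeping formalin-fixed, paraffin-embedded biopsies. No extra biopsy, visit or additional slide reader is needed, and sample size and nominal power do not change. Masking to exposure may be only partial because exposed and unexposed skin can look different; masking to visit is what matters. If masked reading is already the laboratory's practice, a sentence saying so settles the point.

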13.4. Analysis Plan

13.4.1. Analysis Populations

The **Safety Sample (SS)** population includes all participants who receive any amount of tofacitinib.

The **Per Protocol 1 (PP1)** population includes all participants who receive any amount of tofacitinib and who complete phototests and skin biopsies at both baseline (Visits 1 and 2) and post-treatment (Visits 4 and 5) time points. Only individuals who complete at least 21 days of IP dosing will have the post-treatment phototest. The primary objective of this proof-of-concept study cannot be evaluated in individuals who do not have data at both pre- and post-treatment time points.

The **Per Protocol 2 (PP2)** population includes all PP1 participants with no protocol deviations that would impact photo sensitivity assessments. The reported major deviations will be reviewed during a masked data review to determine which participants should be excluded from the PP2 population.

